## BACKGROUND/RATIONALE

Posttraumatic stress disorder (PTSD) related to maltreatment is a strong predictor of intergenerational cycles of abuse and vulnerability. These cycles intersect during the childbearing years when unresolved trauma often adversely affects a woman's mental health. Women of color are especially at risk for developing PTSD as well as experiencing disparities related to maternal and infant morbidity and mortality. Pregnancy is an opportune time to intervene to disrupt these cycles, however, screening and treating PTSD in the perinatal period is rarely undertaken. Therefore, readily available interventions for low-resourced and high-risk settings are warranted. Our agency, Buffalo Prenatal Perinatal Network (BPPN) provides home visiting and other supportive services to pregnant women and their families who bear considerable burden of poverty, adversity, and disparities. As such, we are well positioned to conduct research to address perinatal PTSD. Our previous research has established initial acceptability and feasibility for a novel front-line PTSD-specific perinatal intervention, the *Survivor Moms' Companion (SMC)*. In the proposed study, we will advance this trajectory of research and build our capacity for mental health service provision by conducting an initial randomized controlled pilot study.

### PTSD and the Childbearing Year

In the U.S. and globally, approximately 20% of women experience sexual violence and other forms of maltreatment, including childhood physical, sexual, emotional abuse and neglect. Unresolved reactions to trauma can manifest as PTSD and its complex forms or comorbidities. Rates of childhood trauma exposure may be even higher in pregnancy, with 35% of pregnant women reporting at least one type of childhood abuse or neglect. As a result, PTSD incidence is higher during pregnancy (8%) than at any other time during the lifespan (5%), and increases risk for adverse outcomes including lower birth weight and shorter gestation, less breastfeeding, postnatal PTSD and depression, impaired bonding, less sensitive parenting, a dysregulated infant, and more protective service involvement. This affirms the need to address PTSD with trauma-exposed mothers in order to help prevent negative intergenerational effects.

### Disparities in Risk

African American families in particular are disproportionately affected by maternal and infant morbidity and mortality. However, pregnancy PTSD remains an understudied area of health disparity. African American women bear a four-fold greater rate of PTSD in pregnancy compared to all other groups (13.4% vs. 3.5%). This is likely due to disproportionate exposure to racism, discrimination, and violence. In prior research by our team, this disparity was evidenced in multivariate models that took race/ethnicity and maltreatment-related PTSD into account, finding PTSD was a significantly stronger predictor of shorter gestational age than African American race and was a nearly equal predictor of decrements in birthweight. Therefore, addressing PTSD with pregnant African American women has the potential to reduce disparities in prematurity.

### Addressing Perinatal PTSD

Addressing trauma and PTSD has been identified as a public mental health priority. However, currently in the U.S., maternity services focus on depression and do not address PTSD, despite there being a high rate of comorbidity between perinatal depression and PTSD (~50%). Although there are some existing programs for women with maltreatment histories, these have not been designed to address the specific needs of those with PTSD in the perinatal period and are not integrated in maternity care. Further, treatment of PTSD during pregnancy is hindered by several potential barriers including the lack of screening, lack of readily available behavioral health resources, stigma around seeking help, lack of cultural consideration, unacceptability due to navigating simultaneous demands of pregnancy, transportation, child care, and the high cost of mental health counseling. Our proposed research provides opportunity to evaluate the first intervention specifically designed to address PTSD in pregnant women, the *Survivor Moms' Companion*.

The *SMC* is designed for low-resourced settings and includes provision of information regarding the negative effects of PTSD during the perinatal period, incorporates skill building for managing traumatic reactions, and provides emotional support via client/interventionist discussion sessions. The *SMC* utilizes best practices for behavioral therapies development including that it: (a) was designed with input from target clients and clinicians, (b) is manualized per NIH workgroup best practices for behavioral interventions, and (c) has strong support for acceptability in preliminary studies. The *SMC* focuses on helping women manage PTSD symptoms in the presence of specific childbearing triggers, such as fear of labor pain, and promotes maternal development by anticipating parenting concerns, such as feelings elicited in response to infant crying. The

SMC is also designed to target theorized mechanisms that maintain PTSD, including intrusive re-experiencing, hyperarousal, avoidance, and emotion dysregulation and interpersonal sensitivity.

Our team conducted an initial pre- to post-test pilot of the SMC at BPPN from June 2018 to December 2019. Ahead of implementation we engaged in community-based participatory research to optimize the SMC for our specific context. We recruited 56 women to the pilot; our sample included majority African American (57%), European American (18%), Latinx American (21%), Asian American (2%) women, and those identifying more than one race/ethnicity (9%). The entire sample struggled with poverty, and the vast majority reported having experienced 4 or more childhood adversities, which has been identified as placing individuals at high-risk for a variety of poor physical and mental health outcomes. All participants had clinically significant PTSD.

Table 1: Pre-posttest results of the Survivor Moms' Companion initial pilot study at BPPN in Buffalo, NY				
Measure	n	M	SE	P
PTSD symptom severity (PCL-5), range 0-80 a	56			
Pretest		38.98	2.54	<.001
Posttest		23.69	1.91	
Depression (EPDS), range 0-30 b	56			
Pretest		14.20	0.83	<.001
Posttest		9.15	0.64	
Anger (STAXI-AX), range 0-24 c	56			
Pretest		18.02	0.93	.02
Posttest		16.12	0.65	
Interpersonal Sensitivity (SCL-90), range 0-36 d	56			
Pretest		17.73	1.40	<.001
Posttest		10.11	0.90	

a PTSD Checklist for DSM-5  
b Edinburgh Postnatal Depression Scale  
c State Trait Anger Expression Inventory  
d Symptoms Checklist-90 Revised/Interpersonal Sensitivity Subscale

Intent-to-treat analyses (**Table 1**) showed improvements in PTSD symptom severity, interpersonal reactivity, and two indicators of affect dysregulation: anger expression and depression. The findings were also *clinically* important; for the per protocol sample at pretest, 25 individuals had symptom severity scores indicating they were in the clinical range for meeting PTSD diagnosis; at posttest, only 9 of those individuals remained in clinical range. Qualitative analysis found the SMC was highly acceptable, with the majority of clients indicating they would do it again if given a chance and would recommend it to others. They expressed appreciation in a variety of ways, including that “the SMC made me realize that not all has to be looked at in a negative way,” and that “without the support I got from BPPN and the SMC, I don’t know how I would have gotten through with this pregnancy.”

Given the burden of PTSD among our clients, and these promising results, we propose a pilot randomized trial as the next logical step toward evaluating the SMC. We also wish to expand and improve our capacity to continue to conduct clinical research and to deliver and sustain the

SMC through dedicating staff exclusively to the delivery and maintenance of the program.

## Relevance

This proposed study is relevant for the following reasons: 1) it is designed to meet the needs of the 1 in 5 pregnant women with a childhood maltreatment history; 2) it has the potential to reduce perinatal racial disparities related to PTSD symptomatology and poor outcomes; 3) it advances PTSD-specific care in the perinatal period; 4) it has strong theoretical underpinnings; 5) and it has the potential to play a significant role in preventing potential childhood adversity. Finally, this study will provide for the sustainability of the SMC at BPPN and help address the needs of our at-risk clients. Positive findings from this preliminary efficacy trial would advance the evidence base for the SMC and holds promise as a first step toward addressing intergenerational negative outcomes that result from maternal PTSD.

## Proposal Aims

Our specific research aims are:

**Aim 1:** Examine feasibility of the SMC by tracking participant engagement, accrual, and retention rates.

**Aim 2:** Evaluate the preliminary efficacy of the SMC for reducing PTSD symptomatology as compared to the waitlist control group. **Hypothesis:** At posttest, intent to treat analyses will show that participants in the SMC intervention condition will have significantly lower levels of PTSD symptomatology as compared with participants in the waitlist control group.

**Aim 3:** Assess acceptability of the SMC through post-intervention assessment feedback and evaluation of lost-to-follow-up rates.

**Aim 4:** This exploratory aim will examine how changes in the theorized targeted mechanisms (i.e., emotion regulation, and interpersonal sensitivity) mediate the relationship between the intervention and PTSD symptomatology. **Hypothesis:** At posttest, intent to treat analyses will show that participants in the SMC

intervention condition will have lowered levels of emotion dysregulation and interpersonal sensitivity as compared with participants in the waitlist control group.

## RESEARCH ACTIVITIES

### Study Overview

To achieve these aims, we will conduct a pilot randomized controlled trial. For Aim 1, we will assess feasibility of the *SMC* intervention through tracking and close monitoring of participant engagement, accrual, and retention rates. For Aim 2, we will conduct baseline assessments for all participants for trauma, PTSD diagnosis and symptoms, affect regulation including depression, anger expression, dissociation, and emotion regulation, as well as interpersonal sensitivity. We will then randomize participants to either the *SMC* intervention group or to the waitlist control group. Those in the *SMC* intervention ( $n = 30$ ) will receive a minimum of 4 *SMC* modules and corresponding weekly sessions with an interventionist prior to completing the post-intervention assessment. Those in the waitlist control ( $n = 30$ ) will complete a post-intervention assessment at 6 weeks following their baseline assessment and will then be offered the *SMC* intervention. We will use intent-to-treat analyses to evaluate the preliminary efficacy of the *SMC* for reducing PTSD. For Aim 3, we will examine post-intervention indices of client satisfaction and evaluation of drop-out rates. For Aim 4, we will examine how changes in the theorized targeted mechanisms mediate the relationship between the *SMC* intervention and PTSD. We will utilize knowledge gained to prepare applications for continued evaluation of the impact and implementation of *SMC*. Prior to beginning any study activities, we will apply for approval with the Institutional Review Board (IRB) at the University at Buffalo and will require human subjects training for all study team members through the Collaborative Institutional Training Initiative (CITI Program).

### Participants

**Recruitment Site and Sample Size.** We will recruit pregnant participants at BPPN, which provides services to over 800 families per year; services begin in pregnancy and include screening for risk factors and stressors and supportive home-based services. Consistent with the NIH-wide initiative to increase diversity in research, recruiting at BPPN ensures representation of women of color. Based on the previous *SMC* pilot studies, we expect that 30% who initially consent to the study will not complete the full 4 intervention sessions. We plan to enroll and randomize 78 participants to retain 60 (30 *SMC*, 30 waitlist control).

**Eligibility Criteria.** Inclusion criteria are: (1) English-speaking, (2) currently pregnant and after 12 weeks but before 30 weeks gestation to allow for study completion prior to expected delivery, (3) aged 18 and older, (4) a history of trauma and PTSD, (5) able to comprehend the study protocol, consent form and provide written consent, and (6) able to commit to a minimum of 4 weekly intervention sessions. Exclusion criteria are: (1) non-English-speaking, (2) less than 18 years of age, (3) those with psychotic conditions or developmental disabilities requiring guardianship, (4) those with high-risk pregnancies necessitating extended bedrest or inpatient care, and (5) those unable to commit to completing the intervention sessions.

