### Study Procedures

For Aim 1, we will maintain a master tracking file that indicates mode of invitation (handouts or flyers, word of mouth), screening and determination of eligibility, random assignment to *SMC* or waitlist control, receipt of informed consent, mode of delivery (in-person or by telehealth), and completion of assessments and intervention sessions. We will also track *SMC* uptake for waitlist controls, who will be invited to begin the *SMC* 6 weeks following baseline and immediately following the post-intervention assessment. We will enroll 3-4 participants per week (divided between intervention and control groups) during the active recruitment period.

For Aim 2, our procedures include baseline assessment for all participants, randomization to *SMC* or the waitlist control group, provision of a minimum of 4 *SMC* sessions for those in the *SMC* intervention arm, and post-intervention assessments (for both *SMC* and waitlist control groups).

For Aim 3, we will assess the acceptability of the *SMC* through post-intervention assessment feedback and through evaluation of lost-to-follow-up rates.

For Aim 4, we will examine how changes in the theorized targeted mechanisms mediate the relationship between the intervention and PTSD symptomatology, using the same assessment data utilized for Aim 2.

**Recruitment Strategy.** We will disseminate study information to all BPPN clients through informational handouts and fliers. Those interested will be invited to contact the licensed master social worker (LMSW) for screening. Women who meet all inclusion criteria and no exclusion criteria will be provided with a detailed explanation of the study, and will be encouraged to ask questions prior to providing written consent. They will then be invited to complete the baseline assessment with the LMSW. Once baseline assessment is completed, participants will be: 1) randomized to the *SMC* or waitlist control arm in a 1:1 fashion using a block randomization scheme, 2) will be mailed the *SMC* materials and 3) be assigned to the community health

worker (CHW) who will contact the participant and arrange the first session, either in-person or remotely according to the participant's preference. Consent forms will outline remuneration for each aspect of the study (\$30 for the baseline and \$40 for the post-intervention assessments).

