## Measures

We plan to use reliable and valid measures, these and their schedule of use are listed in **Table 2**. For **eligibility screening** we will use the 5 sentinel items from the Childhood Trauma Questionnaire (CTQ), and the Primary Care PTSD Screen for DSM-5 (PC-PTSD-5). For the **baseline assessment** we will assess trauma exposures, PTSD and its dissociative subtype, and measurements related to the theorized mechanisms of change, including for affect regulation and interpersonal sensitivity. All of these will be repeated at the **post-intervention assessment**. Also, at post-intervention, participants in the SMC arm will complete the

Client Satisfaction Questionnaire (CSQ-8), and invite feedback regarding perception and experience of in-person vs telehealth sessions based on their choice of modality. For those in the SMC arm we will utilize two measures during each weekly intervention session: SMC fidelity checklists, as well as Subjective Units of Distress (SUD). The SUD will be assessed on a 0-10 scale by asking the participant to rate any distress experienced ahead of session, at mid-session, and at the close of the session. Those with SUD rating of 5 or above at the session's end will be encouraged to participate in a brief relaxation exercise until their rating is reduced to 4 or lower. All who complete baselines and are randomized will be scheduled for the post-assessment; those who fail to complete will be scheduled based on their anticipated completion date.

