### **Proposed Analysis**

**Data Quality Management.** Biostatistician [name] and PI [name] will oversee data collection, management, and storage using UB's established IT infrastructure. A created Data Management Plan will track any critical milestones and data review activities. A full study build will be implemented with use of REDCap and all necessary electronic case report forms (eCRFs) will be created in direct contact with relevant study personnel. Rigorous quality control procedures will be implemented so as to ensure data integrity.

**Effect Size and Power Calculations.** Because data will be generated as part of a pilot case-control study, our hypotheses should be viewed as exploratory. Analyses will be conducted to not only test the predictions, but also to examine effect sizes. If effects are clinically meaningful, effect sizes will be used to inform power calculations for a larger, planned Stage II clinical trial.

**Data Analyses.** The amount and nature of missing data for study variables will be characterized and no method of imputation will be used for missing data for primary analyses. The robustness of primary results will be assessed using several statistical techniques including multiple imputation. Outcome variables will be summarized overall and by relevant demographic and baseline variables. Descriptive statistics will be computed for all categorical variables. Numeric variables will be summarized using mean, standard deviation and range. Statistical tests will be carried out using SAS version 9.4 (or higher) statistical software (Cary, NC).

**Aim 1 Analyses.** Feasibility will be assessed via timely recruitment of participants, and through high study retention (70%). This will be carefully tracked and monitored closely by the Co-PIs.

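### The plan's only stated loss rate, 30%, does not turn 78 randomised into 60 retained; that step needs a loss of about 23%, which is stated nowhere

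*Combined protocol and SAP*

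**What the plan says.** The sample size paragraph under Participants rests on two consecutive sentences. The first, citing earlier pilots, gives the expected loss: "we expect that 30% who initially consent to the study will not complete the full 4 intervention sessions". The second gives the target: "We plan to enroll and randomize 78 participants to retain 60", split as 30 SMC and 30 waitlist control. Risks/Blockers and Mitigation Strategies repeats the step from 78 to 60.

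The Study Overview attaches the two groups of 30 to different events. For the intervention arm: "Those in the *SMC* intervention ( $n = 30$ ) will receive a minimum of 4 *SMC* modules". The 30 waitlist participants "will complete a post-intervention assessment at 6 weeks following their baseline assessment" and are offered the SMC only afterwards.

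On sequence, Study Procedures places consent and the baseline assessment before allocation: "Once baseline assessment is completed, participants will be: 1) randomized to the *SMC* or waitlist control arm in a 1:1 fashion". On follow-up, Measures says: "All who complete baselines and are randomized will be scheduled for the post-assessment".

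Aim 1 Analyses takes 70% study retention as a mark of feasibility. Aim 2 Analyses is by intent-to-treat. The section on effect size and power calls the hypotheses exploratory and sets no power target.

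**The concern.** The 30% and the 78-to-60 step stand next to each other, so a reader takes the second to follow from the first. It does not: a 30% loss from 78 leaves about 55, not 60. No other expected loss rate is given, either for the waitlist arm or for the post-intervention assessment, so the 60 has no stated basis.

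What is at stake is how well the plan forecasts its own yield. Feasibility, including retention, is Aim 1, and 60 is the number the sponsor will be held to. If the 30% expectation proves right among those randomised, the study could miss 60 while behaving exactly as forecast.

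**Working it through.** **Inputs from the documents**
- Randomised: 78; retained: 60, 30 per arm (Participants; 78 to 60 repeated under Risks/Blockers)
- Expected loss: 30% of those consenting do not complete four sessions (Participants)
- Allocation: 1:1, so 78/2 = 39 per arm (Study Procedures)

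**Step 1. Try to reproduce the plan's figure.** To retain n after a loss d, randomise n/(1 - d).
- 60/0.70 = 85.7, so 86, against the stated 78.
- Loss applied to the SMC arm only: 30/0.70 + 30 = 72.9, so 73 to randomise. Run forward from 78, it gives 27.3 + 39 = 66.3 retained. Neither matches.
- 60 x 1.30 = 78 exactly. Multiplying by 1 + d instead of dividing by 1 - d would therefore give the plan's number. The plan shows no formula, so this origin is an inference.

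**Step 2. Run the stated rate forward from randomisation.** This assumes no loss between consent and randomisation.
- SMC participants completing four sessions: 39 x 0.70 = 27.3, short of 30 by 2.7.
- Both arms, if the waitlist arm is assumed to lose the same share: 78 x 0.70 = 54.6, short of 60 by 5.4.
- If each of 39 completes with probability exactly 0.70, the binomial chance of at least 30 is 0.224.

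**Step 3. Find the loss that the target implies.**
- 1 - 60/78 = 0.231, or 23.1%. The documents state no such rate.

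**Step 4. Allow for loss before randomisation.** The 30% is counted from consent. If a share x of those consenting leaves before randomisation, SMC completers = 39 x 0.70/(1 - x). The values of x are assumptions.

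| Assumed x | Expected SMC completers of 39 |
|---|---|
| 0% | 27.3 |
| 2% | 27.9 |
| 5% | 28.7 |
| 9% | 30.0 |

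At 9%, the number consenting is 78/0.91 = 85.7, about 86.

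**Step 5. Read retained as having a post-intervention assessment.** The number per arm is 39 x (1 - w) for an assumed assessment loss w.

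| Assumed w | Per arm | Both arms |
|---|---|---|
| 10% | 35.1 | 70.2 |
| 20% | 31.2 | 62.4 |
| 23.1% | 30.0 | 60.0 |
| 30% | 27.3 | 54.6 |

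**Step 6. Effect on precision.** With a common standard deviation, the width of the interval for the group difference is proportional to sqrt(1/n1 + 1/n2). Relative to 30 and 30:
- 27.3 and 30: ratio 1.024, so 2.4% wider.
- 27.3 and 27.3: ratio 1.048, so 4.8% wider.

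This applies only if the number assessed falls. Missed sessions alone do not remove anyone from an intent-to-treat analysis.

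**The case against.** The strongest reply is that the 30% and the 60 count different things from different starting points.

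- **Denominator.** The 30% is of those who consent, while 78 is the number randomised. About 86 consenting, 78 randomised and 60 retained would satisfy it. This stands as a possibility. But the plan gives neither a count of those consenting nor a loss before randomisation, so a reader cannot take the 9% from it. Nor does the plan state zero loss, so 27.3 is conditional.
- **Event.** Waitlist participants have no sessions to complete before their post-assessment, so session completion cannot define their 30. This stands too. The total of about 55 needs the extra assumption that the waitlist arm loses 30% at assessment. If retained means assessed in both arms, the 30% is not the relevant rate, and 60 is then unsupported, not miscalculated.
- **Benchmark.** 60 of 78 is 76.9%, above the 70% in Aim 1, so the target does not conflict with that criterion. True, but the 70% is a benchmark, not a forecast, and it does not yield 60.
- **Uncertainty in the 30%.** If the rate rested on 56 women, the size of the pilot described in the background (an assumption), its approximate 95% interval would be 0.30 plus or minus 1.96 x sqrt(0.30 x 0.70/56), or 18% to 42%, which includes 23.1%. The 22% chance in Step 2 should therefore be read loosely. But 23% is not the rate the plan chose to state.

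A reader might go further and infer that the plan itself predicts 27 per arm, that an inflation error has been shown, or that 86 must be randomised. The documents support none of these. The first needs the 30% carried to those randomised and, for the waitlist, to assessment loss. The second is an inference from a numerical match. The third would matter only if 60 were required, and 60 comes from no power calculation.

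**Conclusion.** The sample size statement is wrong as written: the only expected loss rate given does not deliver the stated yield, and the 23.1% that would deliver it is stated nowhere. The shortfall is 2.7 SMC session completers (27.3 against 30) if the 30% applies from randomisation. It is 5.4 participants overall (54.6 against 60) if the waitlist arm is assumed to lose the same share. With loss before randomisation the SMC gap shrinks, and it closes at about 9%.

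The consequence is minor. The hypotheses are exploratory, all randomised participants are scheduled for assessment, and the tracking file already records "completion of assessments and intervention sessions". Precision suffers only if fewer assessments are obtained, by about 2% to 5% in interval width. The plan also leaves undefined what counts as retained, and which count Aim 1 compares with 70%. That is missing detail to settle in the same edit, not a further error.

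**What to change.** Keep 78 randomised and make the Study Overview, Participants and Risks/Blockers sections agree in one of two ways.

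1. Restate the expected yield as about 27 per arm, about 55 in total (54.6 before rounding), at 30% loss, saying that the rate is applied from randomisation and assumed for both arms.
2. Keep 60, but state and justify a loss of about 23% from randomisation to the post-intervention assessment in each arm. Give SMC session completion as a separate figure: about 27 of 39 if 30% of those randomised do not complete four sessions.

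If the 30% is meant from consent, add the expected loss between consent and randomisation. One further sentence should say which count the word retain refers to and which one Aim 1 sets against 70%; the 70% itself need not change.

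The cost is wording only, with no added participants or data. The first option shows a slightly less favourable yield. The second commits the sponsor to an assessment loss rate that it must defend.
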